All nine patients who reported pain at the beginning of the study reported reduction from scores of 7 to 10 to scores of 0 to 3 at study end. The barrier film was therefore able to provide substantial pain reduction in all patients who reported pain at enrollment, with reduction of patient scores from 7-10 at Day 1 to 0-3 at study end. The protective nature of the barrier film with skin healing reduced reported pain scores during cleansing and subsequent product applications.

There were no reported adverse events associated with the barrier film application. The formulation was able to polymerize and able to create a protective barrier in the presence of oozing exudates and blood.

This product has also been tested in hairless guinea pig and Yorkshire pig models. These studies have demonstrated the formulation's ability to protect Dermatome created superficial wounds from an artificial intestinal fluid for up to 96 hours, and allow healing under continued exposure to the artificial intestinal fluid. In porcine partial thickness wounds, the formulations were able to polymerize and

create a barrier in the presence of exudate and blood, demonstrating hemostatic and lymphostatic properties.

Ten (10) human clinical studies have been completed on healthy subjects, with the product being applied to the back, arms, and buttocks. No adverse events were reported, and no irritation or sensitization was observed in single or multiple dose (N=5 doses on buttocks) in studies involving healthy subjects. The product was well tolerated. A product durability study was completed with the final dosing recommendation of twice a week to three times a week dosing depending on whether there is intact or partial denuded skin.

5. Study Objectives and Purpose

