	Category 2 - Red* with skin breakdown (moderate-severe)	As above for Category 1 +/-vesicles/bullae/skin erosion +/- denudation of skin +/- skin infection

If a subject does not meet all the Inclusion/Exclusion criteria, and is excluded from the study, the reason(s) for exclusion will be documented on the Screening Log.

If a subject meets all the Inclusion/Exclusion criteria, the Investigator or study nurse will obtain and open the randomization envelope to determine which product group the subject has been assigned to. The study nurse will complete the following remaining screening activities:

- Record subject demographics.
- Obtain and record IAD history.
- Obtain and record information describing current medications and IAD treatment.
 - Oral or systemic medications prescribed by the subject's physician are allowed and will be noted on the appropriate CRF.

- Incontinence-related devices (such as urinary catheters, pads, diapers, etc.) are allowed and will be noted on the appropriate CRF.
- Use of moisture barrier, creams, ointments, pastes, or other topical medications in combination with the Cavilon Advanced Skin Protectant product for the management of IAD is **not** allowed.
- If subjects had prior barrier film products on their skin, use the Brava Adhesive Remover Wipe.
- Conduct pressure ulcer risk assessment using Braden Scale.
- Administer Quality of Life questionnaire.
- Perform skin cleansing:
 - Use 3M[™] Cavilon[™] No-Rinse Skin Cleanser (to be provided by 3M) or warm tap water and soft cloths.
 - Avoid rigorous scrubbing to minimize friction damage.
 - Record pain score assessment using Faces Pain Scale Visual Analog before and after cleansing for adults or the FLACC scale for pediatrics during the cleansing process.
- Conduct skin assessment:
 - Complete a skin assessment of the following six zones for its color, presence of lesions, and skin loss. Only subjects with denuded skin may be enrolled. The IAD score will be calculated electronically once results are entered into computer system using 3M's validated Skin Condition Assessment Tool (see Appendix A).
 - Zone 1: Includes the anus and 2 inches surrounding anal opening plus: for males score the scrotal sac and females the labia majora.
 - Zone 2: Crease between buttocks, above the anal opening and 2-3 inches below natural waistline
 - Zone 3: Left buttock starts above fold between thigh and buttock and extends upward to 2-3 inches below natural waistline

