 - At each incontinence care episode, cleanse the skin with 3M[™] Cavilon[™] No-Rinse Skin Cleanser or warm tap warm with soft cloths. Gently dry. Avoid rigorous scrubbing to minimize friction damage.
 - Do not reapply Cavilon Advanced Skin Protectant between each incontinence cleansing episode. Follow the dosing schedule of either:
 - M-W-F, T-TH-Sat, W-F or TH-Sat for week 1. Week 2 &3 follow M-W-F.
 - For the comparative arm product must be applied at every incontinence cleansing episode.
- Healthcare Worker Ease of Use Survey (only after first dosing)
 - Complete product Ease of Use survey following application of Cavilon Advanced Skin Protectant
- Cavilon Advanced Skin Protectant Product Application
 - Following cleansing, the 3M[™] Cavilon[™] Advanced Skin Protectant will be applied 3 times a week following the M-W-F dosing schedule.
 - A thin coat of the Cavilon Advanced Skin Protectant will be painted on or dabbed onto the area covering the entire 6 zones. The Cavilon Advanced Skin Protectant product contains 2.4 mL of material which can cover a maximum area of 25 cm X 25 cm or 10 inches X 10 inches.

- More than one applicator may be necessary depending on the surface area involved. In the event that the contents of one applicator are not sufficient to cover the area requiring protection, additional applicators can be used as needed. Record the number of applicators used.
 - For subjects with IAD in the perineal area (front of body), the same product (either Cavilon Advanced Skin Protectant or comparative product) should be applied in the perineal area. This area will not be graded for IAD, but application of product in this area will be noted on the case report forms and the number of applicators used for the perineal area will be tracked separately from the applicators used on the buttocks.
- If there should be a need for product removal, use adhesive remover and gently wipe the area.
- Document the amount of product required to cover the entire affected area
- Record pain score using Faces Pain Scale Visual Analog before and after product application
- Clean Trace ATP System Evaluation after Sensi-Care Product Application
 - After all photos, patient assessments and after product application are completed, the Sensi-Care tube of paste used will be swabbed for environmental contamination using 3M Clean Trace ATP System.

• ConvaTec Sensi-Care® Protective Barrier Paste Application

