- Pain scores during incontinence management will be measured on a 0-10 scale, and will be analyzed only for those subjects from the ITT dataset who can report pain. This dataset will exclude those who are paraplegic or cannot respond. Infant pain will be measured with the FLACC tool⁴², and adults with the 0-10 Faces tool, and the data will be combined for statistical analysis. For this dataset, the pain scores will be compared by day using an analysis of variance with center, product, age group (infants vs adults), and interactions as factors in the model. If the age group-by-treatment interaction is significant (P<0.05), the data will be analyzed by age group. This response will be considered significant using a Hochberg's procedure for adjusting the P-values for this and the other secondary response of time to re-epithelialization.

- The proportion of subjects on each treatment group with stinging or burning upon application will be compared using a Cochran-Maentel-Haenzel test, stratifying for center.
- Percent change in IAD scores at each visit.
- Efficacy in subjects who switch from the comparative product to the investigational product after failure on the comparative product. For this analysis, the proportion of subjects with resolution of IAD as defined above will be estimated.
- Prevention of IAD in areas that had no denuded skin and remained free of IAD throughout the intervention. This will be estimated and tested using a Cox Proportional hazard model.
- Prevention of IAD, as measured by IAD scores in subjects whose IAD re-epithelialized and who continued on the investigational product. The proportion of subjects who have no progression of IAD, while still experiencing incontinence, will be estimated.
- Patient Quality of Life (QoL) as measured by the EQ-5D-5L questionnaire will be analyzed by comparing the change from baseline in each of the domains. The changes from baseline will be compared using an analysis of variance with center, product, type of skin (denuded or not), and interactions as factors in the model.
- Nursing time will be summarized for a fecal episode occurring post Dose 1 (after first treatment) for a subset of subjects. The nursing times will be summarized for both product groups.
- Incontinence product use will be recorded during the study, and summarized for both product groups. The purpose of this analysis is to provide estimates of total IAD management cost for both regimens.

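### Pain, one of two Hochberg-controlled secondary responses, is compared without the baseline pain score the trial already records, which costs precision but not validity

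*Combined protocol and SAP*

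**What the plan says.** Section 19.1.1 restricts the pain analysis to ITT subjects who can report pain. It then states that "the pain scores will be compared by day using an analysis of variance with center, product, age group (infants vs adults), and interactions" as model factors. Infants are scored on FLACC, "adults with the 0-10 Faces tool, and the data will be combined for statistical analysis". The ages are separated only if the age-by-treatment interaction is significant at 0.05.

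Pain carries formal weight: it is to be "considered significant using a Hochberg's procedure for adjusting the P-values for this and the other secondary response of time to re-epithelialization".

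A baseline exists. Among the screening activities in Section 10, pain is recorded "using Faces Pain Scale Visual Analog before and after cleansing for adults or the FLACC scale for pediatrics during the cleansing process". This comes after the randomization envelope is opened but before product is applied under Section 11.1.

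Other outcomes in Section 19.1.1 do use the baseline. The primary endpoint is percent change in IAD score, and the EQ-5D-5L domains are compared as changes from baseline.

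**The concern.** A pain score on a later day probably depends in part on how painful the skin was at entry. The trial measures that at the first cleansing and then leaves it out of the model, so the variation it could explain stays in the error term. Section 5 expects the new product to make care more comfortable by reducing IAD pain, so this comparison supports one of the claims the study is meant to test. The number of subjects able to report pain may also fall below 51 per arm. At stake is a wider confidence interval and lower power than the collected data allow.

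**Working it through.** **Inputs.** From the documents: 51 per arm, 1:1 allocation and a two-sided alternative (Sections 6.1, 6.3 and 19.2). Not in the documents: a pain SD, a target pain difference, or the correlation r between screening and later pain. I take r = 0.3, 0.5 and 0.7 as assumptions, read as the correlation left after site, product and age group.

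**The plan's own figure.** Section 19.2 gives power only for the primary endpoint (difference 45, SD 70, at least 80%).

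- Standard error: 70 × √(2/51) = 13.86.
- 45 / 13.86 = 3.246, and 3.246 − 1.960 = 1.286.
- Power: Φ(1.286) = 0.901.

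The statement holds as a lower bound, but it says nothing about pain.

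**Effect of adding baseline pain.** The variance of the product contrast is multiplied by 1 − r². To express this as power, take the effect that the raw-score comparison detects with 80% power at two-sided 0.05: (1.960 + 0.842) × √(2/51) = 0.555 SD. With adjustment, power for that effect is Φ(2.802/√(1 − r²) − 1.960). At r = 0.5 this is Φ(3.235 − 1.960) = Φ(1.275) = 0.899.

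| Assumed r | Variance removed (r²) | Unadjusted ÷ adjusted variance | Power, adjusted, 51 per arm | Per arm for 80% power, adjusted |
|---|---|---|---|---|
| 0 | 0% | 1.00 | 80.0% | 51 |
| 0.3 | 9% | 1.10 | 83.6% | 47 |
| 0.5 | 25% | 1.33 | 89.9% | 39 |
| 0.7 | 49% | 1.96 | 97.5% | 27 |

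At 0.025, the stricter Hochberg step, the reference effect is 0.611 SD, and adjusted power is 83.9%, 90.6% and 98.1% for r = 0.3, 0.5 and 0.7. These are two-group normal approximations that ignore the site and interaction terms. The proportion of variance removed does not depend on how many subjects can report pain.

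**Which reading is available, and when.** The sections set side by side:

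- Section 10 (screening): adults before and after cleansing, children during it.
- Section 11.1 (dosing-day cleansing): instrument given by age, with no timing for either.
- Section 11.1 (time-and-motion subjects): both instruments, during cleansing and at application.
- Section 11.1 (Cavilon application): "Record pain score using Faces Pain Scale Visual Analog before and after product application", with no FLACC counterpart in that bullet. The Sensi-Care instruction is similar.
- Section 11.2 (final visit): before and after cleansing, with no distinction by age.
- Section 19.1.1: does not say which of these readings is the daily outcome.

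A baseline covariate therefore needs a named reading for each instrument, and so does the outcome it is paired with.

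**The case against.** The strongest reply is that randomization already protects this comparison. That is right. A reader might infer that, without adjustment, a chance difference in entry pain would pass as a product effect. The documents do not support this as a flaw in validity: the unadjusted contrast is unbiased, and chance imbalance is already covered by the nominal error rate. What remains is lost precision.

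A second reply is that the gain cannot be sized. This also stands in part, because every figure for r is assumed. Nor does the visible text show that entry pain varies widely. The account of earlier clinical use before Section 5 says "All nine patients who reported pain at the beginning of the study reported reduction from scores of 7 to 10", which is a narrow range. If these were whole-number scores, the largest possible SD is about 1.6: four at 7 and five at 10 give variance 9 × (4 × 5/81) × 9/8 = 2.5. With that SD, the standard error of a chance baseline difference is 1.58 × √(2/30) = 0.41 to 1.58 × √(2/51) = 0.31 points for an assumed 30 to 51 reporters per arm. An assumed SD of 3 would give 0.77 to 0.59. The proportional gain r² does not depend on the SD, although a narrow spread at entry would tend to lower r.

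A reader might also infer that the analyzed scores mix adult before-and-after readings with pediatric during-cleansing readings, since the instruments are pooled. That contrast is explicit only at screening, and screening scores are not in the model. Nor does Section 19.1.1 say that application scores are merged with cleansing scores. The documents show only that the reading is not named. The age-group factor absorbs a difference in level between the instruments.

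Finally, Section 19.1.1 defers detail to an approved SAP, and no separate one is in the supplied text. If that SAP already names the covariate and the reading, only alignment of the protocol is needed.

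**Conclusion.** The point holds as one of efficiency. A Hochberg-controlled response is analyzed as raw daily scores while a pre-product baseline, already collected, goes unused. On assumed correlations of 0.3 to 0.7, adjustment would remove 9% to 49% of residual variance. This would raise power from 80% to between 83.6% and 97.5% for an effect of 0.555 SD at 51 per arm. If the correlation is 0 there is no gain. The planned test is not biased by the omission, and the documents do not establish a mixture of differently timed readings in the analyzed scores. The change is worth making because it costs almost nothing and the response carries formal inferential weight.

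**What to change.** In Section 19.1.1, add the screening cleansing pain score to the pain model as a covariate, on the subject's own instrument. Name one adult Faces reading (for example, the one after cleansing) and the pediatric FLACC reading. Use the matching cleansing reading as the daily outcome, and keep scores taken around product application out of that test and report them separately.

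The cost is one covariate and a sentence naming the readings, with no new visit or instrument. The covariate can be applied to subjects already enrolled wherever the score was recorded. There are three limits:

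- Subjects with no baseline score need a simple rule stated in advance.
- The daily test will use fewer of the recorded scores.
- Section 10 places the baseline score after the envelope is opened, and Section 6.2 says that the nurse applying product cannot be blinded, so knowledge of allocation could affect the score. Where still possible, record it before the envelope is opened. This cannot be changed for subjects enrolled under earlier protocol versions.

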19.1.2 Safety Analyses

Overall incidence of adverse events will be documented and compared between product groups. This analysis will be carried out for all subjects who are randomized.

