6.4 Study Duration

In order to screen, enroll, and complete 102 evaluable subjects, an enrollment period of approximately 18-24 months is anticipated. Each adult subject may be followed for up to a maximum of 42 days or until the subject is discharged. Each pediatric subject may be followed for up to a maximum of 21 days or until the subject is discharged.

- 1. If the subject is discharged prior to 21 days, the subject will still have met the requirements for study completion.
- 2. Adult Subjects (>18years) can remain in the study for up to 21 days following enrollment receiving the Cavilon Advanced Skin Protectant or comparative product. All subjects will be discontinued at this point with the exception of the following 2 scenarios:
 - Subjects randomized to the comparative group, who fail to reach healing at the end of 21-day period with ongoing incontinence may be crossed over to the Cavilon Advanced Skin Protectant group and allowed to continue for up to an additional 21 days.
 - Subjects randomized to the Cavilon Advanced Skin Protectant group, who either re-epithelized or have a positive reduction in their IAD during the 21-day period, but remain hospitalized and continue to have incontinence, may continue to receive the Cavilon Advanced Skin Protectant product for up to an additional 21 days to evaluate prevention of IAD reoccurrence.
 - If a subject completely heals during the study, they may be discontinued at that time.
- 3. Pediatric Subjects Full term (37 weeks) to 18 years) can remain in the study for up to 21 days following enrollment receiving the Cavilon Advanced Skin Protectant product or comparative product. If the subject is discharged prior to 21 days, the subject will still have met the requirements for study completion.
 - Subjects randomized to the comparative group, who fail to improve (IAD) within 3 days of first application in the study may be crossed over to Cavilon Advanced Skin Protectant group and allowed to continue for up to an additional 21 days. The staff should cleanse the skin, complete skin assessments, and photographs prior to application of Cavilon Advanced Skin Protectant.
 - Subjects randomized to Cavilon Advanced Skin Protectant group, who fail to improve (IAD) within 3 days of first application in the study may be discontinued.

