7.3 Safety Endpoints

Assessment of the safety of Cavilon Advanced Skin Protectant compared to the comparative product will be based upon analyses of the number and percent of subjects with an adverse event (AE) and the nature of each AE. The data will be summarized for each group based on the number and percent of subjects reporting AEs and will be summarized by product group and overall. In addition, AEs will be categorized and then summarized by relation to product and severity/intensity. Incidence of discontinuation will be summarized by reason for discontinuation for each product group.

8. Study Population

The study population will consist of subjects suffering from severe Category 2 Incontinence-Associated Dermatitis where the epidermis has been breached, or the skin is denuded, and who are

in a facility that provides nursing care 24 hours a day. Subjects' incontinence may be urinary and/or fecal, and can be continuous or non-continuous during the 21-day follow-up period. The subjects should not have any pre-existing fungal infections or stage 3, or stage 4 pressure ulcer(s) in the sacrococcygeal and buttock area. Subjects with Stage 1 or Stage 2 pressure ulcers maybe enrolled. (Note, no dressings are allowed for Stage I/II pressure ulcers.) Subjects with ostomies may be enrolled if the anal opening is present and there is evidence of denudement in the perianal or surrounding areas. Also subjects with fecal management systems may be enrolled if there is evidence of denudement in the perianal or surrounding areas. Subjects enrolled must meet the Inclusion/Exclusion criteria set forth in Section 8.1 and 8.2.

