11.2 Final Study Visit

The subject's participation in this study is completed after 21-42 -days of follow-up or when the subject is discharged from the facility. At the final visit the following assessments will be completed:

- Medications
 - Review and record changes to current medications.
- Adverse Events
 - Assess and record adverse events. Immediately report any Serious Adverse Event. (Refer to Adverse Event CRF instructions).
- Perform Skin Cleansing and record pain score before and after cleansing
- Conduct Skin Assessment
- Take Photographs
- Administer Quality of Life questionnaire
- Healthcare Worker Ease of Use Survey
 - Complete end of study product Ease of Use survey
- Documentation
 - Complete and check all documentation.

Page 27 of 54 Status: Release Version: 7 Issue Date: 8/31/2016 12:19:02 PM

Page 28 of 54 Status: Release Version: 7 Issue Date: 8/31/2016 12:19:02 PM

Schedule of Events

Assessment	Screening/ Enrollment	D1 /23	D2 /24	D3 /25	D4 /26	D5 /27	D6 /28	D7 /29	D8 /30	D9 /31	D10 /32	D11 /33	D12 /34	D13 /35	D14 /36	D15 /37	D18 /38	D17 /39	D18 /40	D19 /41	D20 /42	D21 /43	End of Study/ D22/D44
Informed Consent	Х																						
Inclusion/Exclusion	Х																						
Urine Pregnancy Test	X																						
Demographics	X																						
IAD History & Current Product Use	х																						
Medications	Х	Х																					Х
Pressure Sore Risk Assessment	Х																						
Quality of Life questionnaire	x																						X
Skin Cleansing	X	Х	Х	Х	Х	Х	Х	Х	Х	Х	X	Х	Х	Х	Х	Х	Х	Х	Х	Х	Х	Х	Х
*Skin Cleansing – Timing & Product Use	х			X																			
Skin Assessment / IAD scoring	X	X		X		X			X		X		Х			X		X		X			X
Photographs	Х	Х		Х		Х			Х		X		Х			Х		Х		Х			Х
Sensi-Care Product Application Arm		х	X	X	Х	Х	X	X	X	Х	Х	Х	Х	Х	Х	Х	X	X	X	X	X		x
Cavilon Application		Х		Х		Х			Х		Х		Х			Х		Х		Х			
Clean Trace Assessment				X		Х			X		X		Х			Х		X		X			
*Product Application – Timing & Product Use				X																			
Healthcare Worker Ease of Use Survey		Х																					X
Incontinence Episode Care/Tracking		Х	X	X	Х	X	Х	Х	X	X	X	X	Х	Х	Х	X	X	X	X	X	Х	Х	X
Adverse Events		Х	Х	Х	Х	Х	Х	Х	Х	Х	Х	Х	Х	Х	Х	Х	Х	X	Х	Х	Х	Х	Х

* Only required for first Subjects in each product group

12. Subject Discontinuation

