17.4 Risk to Benefit Rationale

The study product is investigational and is classified as non-significant risk. Based on data collected in previous studies, the risk-to-benefit ratio is within reason for foreseeable risks. However, appropriate observation and follow-up of subjects, will still be required as outlined in the protocol.

18. Safety Reporting

Adverse events will be collected for subjects beginning at Day 1 through the final study visit, or until the subject is discharged from the facility. An adverse event is any symptom, sign, illness, or experience, which develops or worsens during the course of the study, which may or may not be considered investigational product related. The principal measures of safety will be the incidence of adverse events reported during the study.

An anticipated adverse event in this study is a skin reaction to the investigative product itself. Worsening of IAD is expected in this subject population and would therefore not constitute an adverse event (related to the product being tested).

The Adverse Event CRF will be used to capture any safety-related concerns.

18.1Adverse Events

The Investigator is responsible for identifying and reporting adverse events experienced by each subject throughout the study. An adverse event can occur at any time during the conduct of the study, in any phase of the study, or after the study is completed. An adverse event can be identified by the Investigator or reported by the subject.

Note: The Federal Privacy Rule (HIPAA) specifically permits the use and disclosure of protected health information "without written authorization of the individual" when used for public health activities such as reporting adverse events, tracking FDA-related products, enabling recalls, repairs, replacements, lookbacks, or conducting post-market surveillance [45 CFR 164.512]. This use and disclosure is subject to the *minimum necessary* standard, i.e. "the minimum necessary to accomplish the intended use, disclosure, or request" [45 CFR 164.502(b)(1)].

An adverse event is considered to be serious if it is:

- Life threatening of results in death
- Causes in-patient hospitalization
- Unduly prolongs hospitalization
- Persistently or significantly disabling
- A congenital anomaly
- Requires intervention to prevent outcomes above

Severity:

All adverse events will be classified as one of the following severities:

Mild: Subject is aware of signs or symptoms but they are easily tolerated.

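### The AE comparison runs to the final visit with no cut at day 21 or at product switch, so paste-arm incidence can include events on Cavilon and the two arms can be counted over unequal time

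*Combined protocol and SAP*

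**What the plan says.** Safety is part of the primary objective (section 5.1). Section 19.1.2 says "Overall incidence of adverse events will be documented and compared between product groups" and adds "This analysis will be carried out for all subjects who are randomized". Section 7.3 fixes the measure: "The data will be summarized for each group based on the number and percent of subjects reporting AEs".

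The collection window is long. Section 18 says "Adverse events will be collected for subjects beginning at Day 1 through the final study visit", or to discharge if that comes first. Section 11.2 says "participation in this study is completed after 21-42 -days of follow-up", again unless the subject is discharged. The CRF table in section 16.3 has the AE form in use for days 23-42.

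Who stays after day 21 depends on arm and outcome (section 6.4):

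- An adult on paste who has not healed and is still incontinent "may be crossed over to the Cavilon Advanced Skin Protectant group and allowed to continue for up to an additional 21 days".
- An adult on Cavilon who has re-epithelialized or improved, and is still hospitalized and incontinent, "may continue to receive the Cavilon Advanced Skin Protectant product for up to an additional 21 days to evaluate prevention of IAD reoccurrence".
- Other adults stop at day 21.
- A child who does not improve within 3 days may switch if on paste, or be discontinued if on Cavilon. Section 12 provides no follow-up after discontinuation.

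No section limits the AE comparison to the randomized period, censors at a switch, assigns events by product in use at onset, or adjusts for time at risk. By contrast, the health economics analysis in section 19.1.3 is confined to three weeks or less.

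**The concern.** A crude percent compares like with like only if each group is observed on its own product for comparable time. Here the period after day 21 contains no paste at all. It consists of improved subjects still on Cavilon and unhealed paste subjects newly on Cavilon. Counted by randomized arm, a reaction to Cavilon in a crossover subject is charged to paste. Counted by product received, Cavilon can accumulate 42 days per subject against 21 for paste.

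At stake is the safety part of the primary objective. A real excess on Cavilon could be diluted, or a difference could appear where none exists. The summaries of fungal infection and pressure ulcer (section 19.1.1) have the same open window. The IAD score endpoint is not the subject of this point.

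**Working it through.** The plan gives no AE rate, exposure figure or safety power, so there is no figure of its own to reproduce. What follows is an illustration on assumed values.

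**Inputs from the documents.** 51 subjects per arm (section 6.3); first period 21 days; adult maximum 42 days in either arm (section 6.4).

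**Assumptions.** Constant AE hazard; *p* = 21-day risk on paste; *R* = true hazard ratio, Cavilon to paste; *f* = share of the Cavilon arm continuing to day 42; *g* = share of the paste arm crossing over and continuing to day 42. Write *q* = 1 − *p*. Continuation is taken as unrelated to AE risk, which is generous to the plan.

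**Counting as randomized, whole period**

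- Cavilon arm: (1 − f)(1 − q^R) + f(1 − q^(2R))
- Paste arm: (1 − g)(1 − q) + g(1 − q^(1+R))

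With *p* = 0.20, *R* = 2 and f = g = 0.50:

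- The 21-day risks are 1 − 0.8² = 0.36 and 0.20, ratio 1.80.
- Cavilon arm, whole period: 0.5 × 0.36 + 0.5 × (1 − 0.8⁴) = 0.5 × 0.36 + 0.5 × 0.5904 = 0.475.
- Paste arm, whole period: 0.5 × 0.20 + 0.5 × (1 − 0.8³) = 0.5 × 0.20 + 0.5 × 0.488 = 0.344.
- Ratio: 0.475 / 0.344 = 1.38.

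Other values at *p* = 0.20:

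| R | f | g | Cavilon | Paste | Ratio, whole period | Ratio, 21 days |
|---|---|---|---|---|---|---|
| 2 | 25% | 50% | 0.418 | 0.344 | 1.21 | 1.80 |
| 2 | 50% | 25% | 0.475 | 0.272 | 1.75 | 1.80 |
| 2 | 10% | 10% | 0.383 | 0.229 | 1.67 | 1.80 |
| 1 | 25% | 50% | 0.240 | 0.280 | 0.86 | 1.00 |
| 1 | 50% | 50% | 0.280 | 0.280 | 1.00 | 1.00 |
| 1 | 50% | 25% | 0.280 | 0.240 | 1.17 | 1.00 |

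With *R* = 2 and f = g = 50%, the ratio falls from 1.90 to 1.44 at *p* = 10%, and from 1.70 to 1.33 at *p* = 30%.

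The share of paste-arm observation time spent on Cavilon is g/(1 + g): 20% for g = 25% and 33% for g = 50%.

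**Counting by product received, equal hazards, *p* = 0.20.** The 42-day risk is 1 − 0.8² = 0.36. Subjects randomized to Cavilon show (1 − f) × 0.20 + f × 0.36, which is 24%, 28% or 32% for f = 25%, 50% or 75%. Crossovers also join the Cavilon group, each with 21 days at risk. If half of the paste subjects cross over (25.5 of 51), the Cavilon figure is (51 × risk + 25.5 × 0.20) / 76.5:

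- f = 25%: (12.24 + 5.10) / 76.5 = 22.7%
- f = 50%: (14.28 + 5.10) / 76.5 = 25.3%
- f = 75%: (16.32 + 5.10) / 76.5 = 28.0%

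Paste stays at 20%.

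**Children.** Section 6.4 contradicts itself: one sentence caps pediatric follow-up at 21 days, while a later item allows up to 21 additional days after crossover. A child who switches at day 3 spends 18 of 21 days (86%) on Cavilon under the first, or up to 21 of 24 days (88%) under the second. Either way, an as-randomized count over the whole period is mostly Cavilon time credited to paste.

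**The case against.** The strongest defence is that the plan does define its groups. In section 10 the randomization envelope determines the product group, section 6.3 enrols 51 in each, and section 19.1.2 analyses everyone randomized. Counting as randomized over the whole period is a recognised choice. That makes the as-randomized reading the likelier one, although section 6.4 also speaks of crossing over to the Cavilon group. The defence settles the grouping but not the dilution.

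Second, a reader might infer that the arms are necessarily observed for different lengths of time, or that Cavilon always has double the time at risk. The documents do not support that. Both adult arms can reach day 42, and mean time differs only if *f* and *g* differ, in either direction. The 42-against-21 contrast holds only by product received, and as a maximum.

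Third, the continuing shares are unknown and may be small. Extension needs improvement, continued hospitalization and ongoing incontinence; eligibility requires only an expected stay of 7 days; healed subjects may leave. This stands, and the 10% row shows a correspondingly smaller effect.

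Fourth, section 7.3 summarizes AEs by relation to product, and section 12 limits pressure-ulcer data to the time before the ulcer and infection data to the time before topical treatment. These help in part. But section 18.2 defines relatedness only against the investigational product, and none of this corrects overall incidence.

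Finally, section 19.1.1 defers analytical detail to a SAP. No safety rule on window or attribution appears in the supplied text, and section 19.1.2 already specifies the comparison.

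**Conclusion.** The point holds in this form: followed as written, the plan compares AE incidence over a period that mixes randomized treatment with selective continuation and, in the paste arm, with Cavilon use. This is more than missing detail.

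On the as-randomized reading, the main effect is dilution: 1.80 becomes 1.38 in the central illustration and 1.67 if only 10% of each arm continue. With no true difference, unequal continuing shares of 25% and 50% give 0.86 or 1.17. On the by-product reading, the spurious Cavilon excess is 22.7% to 28.0% against 20% when half of paste subjects cross over. The 21-day risk, the hazard ratio and the continuing shares are all assumed.

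Two stronger statements should not be drawn. The plan does not say outright that post-crossover events are paste events; that follows from the likelier reading of its grouping. Nor does it establish that time at risk will differ between randomized arms; it only allows it. It should be corrected, but it does not invalidate the trial.

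**What to change.** In sections 7.3 and 19.1.2:

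- Make the between-arm AE and complication comparison by randomized arm, for events with onset from Day 1 to the earliest of day 21, product switch or exit.
- Use events per subject-day as the main measure, with percent of subjects alongside. The percent alone still covers unequal, response-dependent time, because healed subjects may leave early and pediatric paste non-improvers may be cut at about day 3.
- Keep all randomized subjects accounted for in the listings.
- Tabulate extension and post-crossover events separately, by product in use at onset, without a between-arm comparison.
- Reconcile the two pediatric follow-up limits in section 6.4, so that the window is defined for children.

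The cost is analysis wording only. AE onset is already recorded (section 18.2), product application has its own CRF (section 16.3), and the discontinuation date is captured (section 12). There are two downsides. Later events become descriptive. And because cuts at switch or exit depend on response, some informative censoring remains and should be acknowledged when the results are reported.
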